Primary outcomes include process outcomes. The primary outcome of interest is PrEP uptake. Rates of PrEP uptake will be compared in the first 6 months between those in the intervention and control arms; a sensitivity analysis will be conducted to examine de-identified rates of PrEP uptake among others during the same timeframe. Other process outcomes of interest will investigate the reliability of the strategy to 1) deliver an educational PrEP decision

STU#: STU00217596

guide to women with increased vulnerability to HIV, 2) engage those individuals in the PrEP decision guide, and 3) schedule patients for a dedicated PrEP visit

Secondary outcomes include psychosocial outcomes. In post-pilot interviews, we will obtain the following measures. Differences between intervention and control groups will be explored.

The main secondary outcome is PrEP knowledge measured about 2-6 weeks after randomization to the intervention (receiving the materials) or the control (delayed receipt).

Perceived Risk of HIV. We will use the 8-item Perceived Risk of HIV scale to assess how vulnerable an individual feels to HIV. The scale was developed in the United States and attention was paid to health literacy. Response options vary for each item, though they are measured on a 4-point Likert scale.

PrEP Knowledge. We will use a scale created by our team, drawing from the scale previously created by Welsh for use with men.

PrEP Attitudes. PrEP attitudes will be assessed using a recently developed scale developed that includes 5 items, each measured on a 5-point Likert scale (1=strongly disagree to 5=strongly agree).

[figure not shown]
Health Literacy. We will assess health literacy skills via the Newest Vital Sign (NVS).

Participants will be asked to view a nutrition label and to answer 6 questions about how they would interpret the information. Scores are classified as high likelihood of limited literacy (0-1), possibility of limited literacy (2-3), and adequate literacy (4-6). The NVS has a high correlation with the Test of Functional Health Literacy in Adults and includes both reading and numeracy items.

Health Activation. Patients' engagement in their child's healthcare will be measured using a modified version of our team's 10-item Consumer Health Activation Index (CHAI). Response options are a Likert scale; linear transformation is used to put total scores onto a 0-100 scale, with higher numbers indicating greater activation.

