3. Participants will also be asked to view, review, and provide feedback on the draft PrEP decision guide material, including the message informing patients they've received the PrEP decision guide in MyChart and an embedded video.
4. Interviews will focus on the material and are not intended to collect personal information.

[figure not shown]
Procedures for the EHR build. Drs. [name] and [name] (Co-I) will work with NM analysts to build the materials within Epic. Under their direction, clinical informatics staff will build and pilot the strategy in the electronic test environment and implement the strategy after any needed troubleshooting.

Procedures for engaging with the Scientific Advisory Board. During the adaptation phase, we will iteratively work with a Scientific Advisory Board via email and/or videoconferencing platforms for the purpose of obtaining additional scientific guidance on our strategy and content. The board will be comprised of three individuals whose combined expertise will include infectious disease, PrEP, and informatics. The study team will identify individuals with demonstrated expertise through our professional networks at multiple academic institutions and Centers for Aids Research. *This board will also function as a 'mini DSMB'.*

Trial registration. The study protocol will be registered with ClinicalTrials.gov.

Aim 2: Pilot Implementation Phase (Months 10-19)

Procedures for implementing the pilot study. For this 'development of concept' pilot study, the EMC² PrEP strategy will be sent to eligible women over a 6-month period at Northwestern primary care practices.

Approximately 1400 women have been identified as potentially PrEP eligible based on a previous EHR data pull. Women will be randomized 1:1 to either *immediately* receive the EMC² PrEP strategy (intervention; n=700) or a *delayed* invitation (control arm; n=700). In this manner, all patients will have eventually have the opportunity to receive EMC² PrEP materials. Process outcomes may be collected on all these ~1400 women. 100 women per arm will be identified and a

STU#: STU00217596

post-pilot interview conducted to further evaluate intervention effects.

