Procedures for post-pilot interviews (N=200). To further explore intervention effects, the study RC will interview 200 participants approximately 2-6 weeks after they have received the materials or after they have been randomized to the control arm. This includes interviewing 100 participants randomized to the EMC² PrEP strategy intervention arm and 100 randomized to the control arm (delayed invitation).

These patients will participate in an interview lasting ~1 hour. This interview will take place either in person, over the phone, or via a secure videoconferencing platform, depending on patient preferences and the status of the COVID-19 pandemic. However, the last 50 intervention arm participants will have their interviews conducted over a secure videoconferencing platform so that the RA can show them the EMC² PrEP education materials (the PDF and the video) before initiating the interview questions. Cameras will be turned off and there will be no recording. The purpose is just to ensure these participants have had a chance to view the materials before they answer study interview questions. All questions will be verbally asked by the RA as if the participant were on the phone and data will be captured in REDCap per usual. Interviews with both intervention arm (N=100) and control arm (N=100) patients will include quantitative measures assessing perceived risk of HIV, as well as PrEP knowledge, attitudes, stigma, and information sources. Additionally, we will measure health literacy, health activation, and basic demographic information.

Patients enrolled in the intervention arm (N=100) will also complete measures of satisfaction, specific to each strategy component.

Aim 3: Dissemination activities (Months 20-22)

These activities will be the last to occur. First, to obtain feedback from clinicians at a participating NM primary care practice(s), we will speak with clinic staff during an available business meeting after the completion of the pilot study to gauge their reactions to the approach. We will specifically aim to identify clinic-level barriers to implementation of the EMC² PrEP strategy.

The Northwestern research team will then solicit opinions about how best to implement this type of study at AllianceChicago affiliated clinics. To achieve this the research team will speak with current clinic administrators, prescribing providers, or EHR analysts within FQHCs affiliated with AllianceChicago or AllianceChicago itself (N~15).

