Other process outcomes of interest will investigate the reliability of the strategy to 1) deliver an educational PrEP decision guide to women with increased vulnerability to HIV, 2) engage those individuals in the PrEP decision guide, 3) schedule patients for a dedicated PrEP visit, 4) engage patients prescribed PrEP in a portal post-visit treatment initiation questionnaire, and 5) notify prescribers of their patients' treatment initiation barriers. To achieve this, we will identify the percentage of participants randomized to the EMC2 PrEP strategy who complete each step.

Exploratory bivariate analyses will examine whether there are any systematic, statistically significant differences in PrEP knowledge by study arm and between patients who interacted with the PrEP decision guide and those who did not. Specifically, we will use Pearson chi-squared tests or Fisher exact tests for categorical variables and Student t tests for continuous variables. Statistical significance will be defined as $\alpha < .05$.

Confidentiality

Data collected includes consent forms and information collected during the study interviews (demographics, comprehension testing scores, and feedback on the materials). A master study tracking database via REDCap will contain information linking participants to their study ID numbers. This database is secure and only accessible by study personnel. Each participant will be randomly assigned an identification number to ensure confidentiality of data. The RedCap tracking database designed for this study will be the only place where the ID will appear with the participant's name and contact information (address, email, dob, phone number) in the present study. This database will only be accessible by the research team. Survey data and

STU#: STU00217596

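### Staff show the PrEP materials to 50 intervention interviewees, probably within the 6-month uptake window, and the plan does not clearly separate this from the effect of the portal strategy

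*Combined protocol and SAP*

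**What the plan says.** The strategy under test is described under Study Intervention(s) as delivery of a decision guide through the patient portal, with as many as three portal reminders. For allocation, "Women will be randomized 1:1 to either" immediate or delayed receipt ("intervention; n=700", and the same number of controls). Process outcomes may be collected on all of the roughly 1400 women (Procedures for implementing the pilot study).

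Under Study Endpoints, "The primary outcome of interest is PrEP uptake", and "Rates of PrEP uptake will be compared in the first 6 months between those in the intervention and control arms". Quantitative Methods repeats the comparison and makes study arm the covariate of main interest.

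Under Procedures for post-pilot interviews, staff will "interview 200 participants approximately 2-6 weeks after they have received the materials" or after randomization to control, 100 per arm. The section then adds that "the last 50 intervention arm participants will have their interviews conducted over a secure videoconferencing platform so that the RA can show them the" PDF and video before the questions begin. The stated reason is limited to the interview: "The purpose is just to ensure these participants have had a chance to view the materials before they answer study interview questions". No such step is described for controls.

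Study Endpoints also plans a sensitivity analysis of de-identified uptake rates among 'others' over the same period. It does not say who the others are.

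**The concern.** The showing makes sure that 50 women in one arm see the content with a staff member present. The portal strategy does not include that step, and a clinic adopting the strategy would not reproduce it. If it prompts some of these women to seek PrEP, their prescriptions count towards the intervention arm and would be read as an effect of the portal message.

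PrEP uptake may well be rare in this population, although the documents give no rate. With few events, a handful of extra prescriptions can move the risk ratio. The result matters because Aim 2 seeks preliminary efficacy and Aim 3 prepares the strategy for wider use.

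A smaller, related question concerns the process outcome "engage those individuals in the PrEP decision guide". The plan does not say how portal activity by these 50 women after the showing is to be classed.

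**Working it through.** **The plan's own figures.** The documents give no uptake rate, effect size or power calculation. The only figure to reproduce is the allocation: 1400/2 = 700 per arm, which agrees.

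**Share affected.** 50/700 = 7.1% of the intervention arm if all randomized women are analysed. The text says only that process outcomes may be collected on all of them. If uptake were instead compared among interviewees alone, the share would be 50/100 = 50%.

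**Timing.** Take 6 months as 26 weeks and the showing at weeks 2-6.
- If the window runs from each woman's receipt or randomization, 26 − 6 = 20 to 26 − 2 = 24 weeks of it follow the showing.
- If the window is one calendar period, the picture changes. Materials go out over 6 months and these are the last 50 intervention interviewees, so some showings could fall near or after its end.

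The start of the window is not defined.

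**Effect on the risk ratio.** Let p be uptake in controls and in intervention women not shown the materials (so the portal has no effect), and q be uptake in the 50 shown. Then

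RR = (650p + 50q) / (700p) = 1 + (50/700)(q/p − 1).

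Both p and q are assumptions. With p = 1%:

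| q in the 50 shown | Expected prescriptions, intervention v control | RR | Chance of p<.05 |
|---|---|---|---|
| 1% (no effect) | 6.5 + 0.5 = 7.0 v 7.0 | 1.00 | 4.5% |
| 2% (doubled) | 6.5 + 1.0 = 7.5 v 7.0 | 1.07 | not simulated |
| 5% | 6.5 + 2.5 = 9.0 v 7.0 | 1.29 | 7.6% |
| 10% | 6.5 + 5.0 = 11.5 v 7.0 | 1.64 | 17.9% |

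The last column comes from 200,000 simulated trials per row with a Pearson chi-squared test at 5%. The test is taken as two-sided because the protocol does not state sidedness.

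**Range over base rates.**
- p = 0.5%: RR is (3.25 + 2.5)/3.5 = 1.64 at q = 5% and (3.25 + 5)/3.5 = 2.36 at q = 10%. The chance of p<.05 is 9.8% and 26.1%.
- p = 2%: RR is (13 + 2.5)/14 = 1.11 and (13 + 5)/14 = 1.29. The chance of p<.05 is 6.0% and 10.8%.
- If the showing doubles uptake, RR is 1 + 0.071 = 1.07 at any base rate.

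**Cost of the proposed bound.** Suppose the showing does nothing, p = 1%, and prescriptions accrue evenly over 26 weeks. Setting aside those after the showing removes 50 × 0.01 × 20/26 = 0.38 to 50 × 0.01 × 24/26 = 0.46 expected prescriptions. RR falls from 1.00 to between (7 − 0.46)/7 = 0.93 and (7 − 0.38)/7 = 0.95. The bound is therefore mildly conservative in this case.

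**The case against.** The strongest reply is that the magnitude rests on assumptions. Under the scenarios above, q = 5% and 10% at a 1% base mean that the showing multiplies uptake 5- and 10-fold, and nothing in the documents supports multipliers of that size. These women had already been sent the materials through the portal, so the increment is an assured viewing of them. With a doubling, the risk ratio is 1.07. This stands: the direction of a possible distortion is clear, but its size is not.

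A second reply is that a separating analysis may already exist. The Non-consenting patients section uses similar wording for women who get the portal components without being approached for interview. If 'others' means those women, the planned sensitivity analysis is free of the showing. That is a plausible reading, but the text does not say so.

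A reader might also infer three things that the documents do not support:
- *That the 50 women are coached.* The protocol says only that they are shown the materials. It describes no counselling, referral or help with scheduling, and 100 controls have the same interview.
- *That the showing itself counts as engagement.* Under Study Intervention(s), opening and interacting are taken from EHR data. Nothing says that a videoconference display is logged there. At most it could prompt later portal activity.
- *That the 50, or all interviewees, should be dropped from the primary analysis.* Interviewees are selected after randomization, and only the last 50 intervention interviewees need videoconferencing access. The remaining women would not form a randomized comparison.

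**Conclusion.** The point holds as a gap in the analysis plan. An exposure outside the portal strategy is given in one arm only, to 7.1% of that arm if all randomized women are analysed. No text clearly separates its effect on the primary outcome. Most of the uptake window follows the showing if the window runs from each woman's own start date; a calendar window weakens the point.

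A reader might go further and conclude that the uptake result will be spurious. The documents do not support that. With no portal effect and a 1% base rate, the risk ratio runs from 1.00 to 1.64 as uptake among the women shown runs from 1% to 10%, and no figure in the protocol says where in that range, or beyond it, the truth lies. The justified conclusion is that a positive result could not be credited to the portal alone without a further check. In a pilot this calls for a modest, pre-stated addition and no change of design.

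**What to change.** - Keep all of the roughly 1400 women, as randomized, in the primary uptake comparison, and define when the 6-month window starts.
- Record which women were shown the materials and on what date. Do this before the identifying links are removed after data collection (privacy section).
- Pre-specify a sensitivity analysis in which prescriptions to those 50 women after the showing are not counted as uptake. It excludes no one and serves as a conservative bound.
- State that 'others' under Study Endpoints means non-interviewed women in both arms. Report that analysis as supportive only, because interviewees are selected after randomization.
- Report any difference between these results as a limit on attributing uptake to the portal alone.
- For these 50 women, count opening and interacting only from portal logs dated before the showing.

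The cost is a few lines of text, one extra analysis run, and linkage of interview status to the EHR extract. That linkage needs planning, since EHR data are to be evaluated in aggregate and the extract is to hold no identifiable information. The downside is that the bound sets aside some prescriptions that the portal may have earned, so it may understate the effect.

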We will first seek a waiver of HIPPA for recruitment and to be able to send eligible women the PrEP guide via their MyChart. Then, these potential post-pilot interview participants will be identified via the EDW for post-pilot interviews. This list of patient names, medical record numbers, phone numbers, address, and date of birth will be compiled in a report that can be securely accessed and reviewed by study staff. Reports will be run approximately 2 or more times weekly to identify eligible patients.

Similar to the cognitive interviews, recruitment will be done by the RC via telephone rather than by mailing letters. Patients will be called via telephone within approximately 15 days of receiving the materials (randomization to the intervention arm) or randomization to the control arm. Trained RCs will contact identified patients and if they are interested in participating or learning more about the study, the RC will obtain verbal permission to ask the patient a brief series of questions to verify eligibility. If eligible, RC will obtain electronic informed consent. They will then initiate the post-pilot interview or schedule the interview for a time that is convenient to the participant.

COMPENSATION FOR PARTICIPATION IN RESEARCH ACTIVITIES

Study Activity	Payment Amount
Aim 1: Key Informant interviews with clinicians and administrators	\$100
Aim 1: Cognitive interviews with patients	\$30
Aim 2: Post-pilot interviews	\$45

All compensated participants will be paid at the completion of their interview via the PNC Stored Value Visa Card program (physical gift card) or via the Northwestern Visa Prepaid Card program (virtual gift card). At the end of their interview, participants will be asked which payment type they prefer.

WITHDRAWAL OF PARTICIPANTS

There are no anticipated circumstances when a participant would be withdrawn from the study without their consent. Interviews are all conducted at single time-points, therefore participants will not be asked to participate in any subsequent interviews.

RISKS TO PARTICIPANTS

STU#: STU00217596

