Aim 2 Participants. Patient participants who are recruited for participation in the post-pilot interviews (Aim 2) will provide electronic consent with HIPPA authorization. Prior to the post-pilot interview, participants will electronically provide consent. Similar to the consent process for Aim 1, the RC will send patients a link to REDCap by email to be able to read through the consent with the RC. Informed consent will be viewed as a process, i.e. at several times during review of the IRB approved consent document, the subject will be asked to explain in his/her own words what his/her understanding of the consent. This will enable the research personnel to enter into a dialogue with the subject and ensure that the subject understands that he/she is free to withdraw at any time without penalty. Information will be provided to the participants in terms that they can fully understand. There will be no exertion of any overt or covert coercion. They will be encouraged to ask questions prior to giving consent. Participants will be informed about the nature of the study by a CITI certified RC and asked to provide consent. Additionally they will be notified that only those contents of their medical record that are necessary to evaluate the effectiveness of the intervention will be released to the research team at Northwestern. They will be informed that they may withdraw from the study and stop the interview at any time; they will be given contact information for the PI and study coordinator. The patient will then complete an electronic consent and HIPAA Authorization through REDCap. Patients will be informed they can print their screen to keep a copy of the consent, or we can mail or email them a blank copy of the consent document for their records. Prior to completing the phone interview, the RC will review the electronic consent with the patient and confirms the consent was properly signed and completed.

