This study involves the use of Protected Personal Health Information for Aim 2 participants. All enrolled participants in Aim 2 will provide electronic consent with HIPAA authorization for the collection of all data, including review of the patient's medical record.

Waiver of HIPAA Authorization are requested to identify subjects (patients in Aims 1 and 2) prior to enrollment into the study. The following will be collected for eligible patients

- Names
- Street address, city, county, ZIP code
- Date of Birth
- Telephone numbers (home, cell, work)
- Email
- Medical Record Numbers
- HIV testing results
- Sexually Transmitted Testing and/or Illnesses

QUALIFICATIONS TO CONDUCT RESEARCH AND RESOURCES AVAILABLE

The research team is comprised of 5 PhD and/or MD level researchers, and 1 research coordinator (with experience on similar projects). [name] (PI) will manage the team, which includes experts in health literacy ([name], [name]), primary care ([name]; [name]), infectious disease ([name]), HIV prevention and PrEP ([name], [name], [name], [name]) and health information technology ([name], [name]).

MULTI-SITE OR COLLABORATIVE RESEARCH:

STU#: STU00217596

NA

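### Staff recruit, interview and record answers in both arms without masking, so by-arm comparisons of attitudes, stigma, perceived risk and, to a lesser degree, knowledge are open to interviewer effects of unknown size

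*Combined protocol and SAP*

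**What the plan says.** - **Who interviews.** Procedures for post-pilot interviews (N=200) states that "the study RC will interview 200 participants approximately 2-6 weeks after they have received the materials", or after randomization to control, with 100 women per arm.
- **Who recruits.** Under Recruitment Methods, Post-pilot interview participants, "recruitment will be done by the RC via telephone rather than by mailing letters". Women are called "within approximately 15 days of receiving the materials (randomization to the intervention arm) or randomization to the control arm". The team description under Qualifications lists one research coordinator.
- **How answers are obtained.** In the text on the last 50 intervention interviews, "All questions will be verbally asked by the RA as if the participant were on the phone", with answers entered in REDCap in the usual way. The comparison with a telephone interview and the reference to usual practice indicate that the other interviews are spoken too.
- **What differs by arm.** The last 50 intervention women need videoconference access (Inclusion and Exclusion Criteria), and staff show them the PDF and video before the questions. Only intervention women get satisfaction items.
- **What is compared.** The interview covers perceived risk, PrEP knowledge, attitudes, stigma and information sources. Study Endpoints plans to explore arm differences and makes knowledge the main secondary outcome. Quantitative Methods lists knowledge as primary alongside uptake, and specifies Student t tests for continuous variables at 0.05.
- **Safeguards.** Quality Assurance provides for training, a structured electronic survey and certification of interviewers. No section provides for masking the recruiter, the interviewer or the analyst.

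**The concern.** When an interviewer who knows the allocation reads attitude, stigma and risk items aloud and enters the replies, several things can differ by arm: tone, clarification, prompting and the coding of ambiguous answers. Women may also shade their replies on sensitive topics, most plausibly when the person asking has just shown them the educational material. The arm difference would then mix the effect of the strategy with the effect of how it was measured.

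Attitudes, stigma and perceived risk are the most exposed. Knowledge is less exposed if its items are scored right or wrong against a fixed key, but the protocol does not describe the scoring. Because Aim 2 claims preliminary efficacy, these comparisons will be read as evidence about the strategy.

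**Working it through.** **Step 1: what the procedures imply about knowledge of the arm**

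| Interviews | Number | Is the arm known to staff? |
|---|---|---|
| Last intervention interviews | 50 | Yes. Women are screened for videoconference access and shown the materials by staff. |
| Other intervention interviews | 100 − 50 = 50 | Not stated; probably known or discoverable. |
| Control interviews | 100 | Not stated; probably known or discoverable. |

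For the 50 + 100 = 150 interviews where nothing is stated, three features point towards disclosure: the quota of 100 per arm, the intervention-only satisfaction items and the one-coordinator team. In addition, once every remaining intervention woman is shown the materials, a woman interviewed without that step is a control by elimination.

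**Step 2: size, as illustration**

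The documents give no SD, effect size or power for the interview outcomes, so there is no figure of the plan's own to reproduce. Inputs are n = 100 per arm and alpha 0.05 from the protocol. Sidedness is not stated, so two-sided is assumed. The bias b, in SD units, is an assumption. The normal approximation is used.

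- Standard error of a mean difference: √(2/100) = 0.1414 SD.
- Standardized shift: s = b / 0.1414.
- False-positive rate with no true effect: Φ(−1.96 + s) + Φ(−1.96 − s).

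| Assumed bias b | s | False-positive rate |
|---|---|---|
| 0 | 0 | 5.0% |
| 0.05 SD | 0.354 | 6.4% |
| 0.1 SD | 0.707 | 10.9% |
| 0.2 SD | 1.414 | 29.3% |
| 0.3 SD | 2.121 | 56.4% |

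For b = 0.1: Φ(−1.253) + Φ(−2.667) = 0.105 + 0.004 = 0.109. For b = 0.2: Φ(−0.546) + Φ(−3.374) = 0.293.

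If only the last 50 intervention interviews are affected, the arm mean shifts by (50/100) × b. A bias of 0.2 SD in those women then gives a shift of 0.1 SD and 10.9%; a bias of 0.4 SD gives 0.2 SD and 29.3%.

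For scale, the difference detectable with 80% power is (1.960 + 0.842) × 0.1414 = 0.396 SD. A bias of 0.1 SD is about a quarter of that.

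**The case against.** A reader might infer that the coordinator knows every woman's arm from the first call. The documents do not support that. Both arms have the same window of about 15 days from their own starting point, so timing alone does not reveal the arm. The recruitment report is described as holding name, record number, phone, address and date of birth, with no arm field. The position of the satisfaction items within the interview is not stated. Nor is it settled that one person does everything: a sentence in the recruitment section, "Trained RCs will contact identified patients and if they are interested in participating or learning more about the study", uses the plural, and the interview section uses both RC and RA. This part of the objection stands: outside the last 50 intervention interviews, knowledge of the arm is inferred.

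A reader might also infer a demonstrated bias in favour of the strategy. Neither size nor direction is documented. The rates above only restate assumed biases, and part of any wish to please may cancel because staff question both arms about PrEP. This also stands.

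Training, a structured survey and certification do address prompting and inconsistent recording. They standardize delivery but do not conceal the arm.

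Finally, this is a pilot, and the knowledge comparison is called exploratory in one place, although the same section also lists knowledge as a primary outcome. That lowers the stakes without removing the case for an inexpensive safeguard. Showing the materials just before the questions to half of one arm is a separate and probably larger problem, because it changes exposure as well as assessment. Resolving one would not resolve the other.

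**Conclusion.** The point holds as a cheap improvement worth making. Interview outcomes in both arms are elicited and recorded by study staff with no masking. Disclosure of the arm is certain for 50 of the 200 interviews and probable, but not documented, for the other 150. Comparisons of attitudes, stigma, perceived risk and, less so, knowledge are therefore open to interviewer effects of unknown size, likely but not shown to favour the strategy. The false-positive rates of about 11% and 29% rest on assumed biases of 0.1 and 0.2 SD, a two-sided test and a normal approximation; they are not estimates for this trial.

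PrEP uptake and the process outcomes come from EHR data and are not affected. Complete masking should not be expected: neither the last 50 intervention interviews nor the controls interviewed in that phase can be masked.

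**What to change.** 1. For interviews in which staff do not show the materials, give the interviewer a REDCap call list with the due window and no arm. Whoever builds the list holds the per-arm count.
2. In every interview, place the knowledge, attitude, stigma and perceived-risk forms before information sources and satisfaction. Information sources comes later because a woman may mention the guide there. Unlock the satisfaction form and arm field only after the outcome forms are saved.
3. In both arms alike, let women enter the attitude, stigma and perceived-risk items themselves. The route exists: under Consent Process, Aim 2 Participants, "the RC will send patients a link to REDCap by email to be able to read through the consent with the RC". Self-entry does not depend on masking, so it also helps in the last 50 intervention interviews. Keep knowledge items staff-read, verbatim, without prompting and scored against a fixed key, because intervention women could look up answers in the guide in their portal.
4. State in the protocol and the report that masking is partial, and for which interviews.

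The cost is some REDCap build work, and a few women will need items read to them. No extra staff or visits are needed. If interviews have already begun, apply (1) and (2) to those remaining, keep the mode of administration unchanged, and report the lack of masking as a limitation. The last 50 intervention interviews would then gain only the form order, which the limitation should say.

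### The recruitment procedure lets the post-pilot interview start before, or be scheduled after, the approximately 2-6 week window set for the PrEP knowledge outcome

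*Combined protocol and SAP*

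**What the plan says.** Three places in the combined protocol and SAP bear on when knowledge is measured.

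- **Study Endpoints** defines the outcome: "The main secondary outcome is PrEP knowledge measured about 2-6 weeks after randomization".
- **Procedures Involved, post-pilot interviews (N=200)** gives the interview the same timing. The coordinator will "interview 200 participants approximately 2-6 weeks after they have received the materials or after they have been randomized to the control arm".
- **Recruitment Methods, post-pilot interview participants (Aim 2)** governs the contact: "Patients will be called via telephone within approximately 15 days of receiving the materials (randomization to the intervention arm) or randomization to the control arm". After eligibility and electronic consent, the coordinators proceed as follows: "They will then initiate the post-pilot interview or schedule the interview for a time that is convenient to the participant". The same section adds: "Reports will be run approximately 2 or more times weekly to identify eligible patients".

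Three other statements matter. Withdrawal of Participants says each interview is a single time-point with no later one. The Quantitative Methods text lists PrEP knowledge as a primary outcome, whereas Study Endpoints calls it the main secondary one. The interview procedures have the last 50 intervention participants interviewed by videoconference and shown the materials just before the questions.

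**The concern.** The call and the interview are timed from the same starting point, but the call period is almost over when the interview window opens. The recruitment section expressly allows the coordinator to go straight from consent into the interview. It contains no rule to wait for week 2, and its alternative, a convenient time, has no latest date. Because the eligibility report runs at least about twice weekly, women could be identified and called within days of the start.

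An early interview cannot be repeated, because each woman is interviewed once. A knowledge score taken in the first days would still be reported as a 2-6 week result. Intervention women who are not shown the materials at interview would also have had less time to open the guide. Study Intervention(s) allows up to 3 portal reminders, and an early interview might precede some of them; the plan gives no reminder schedule, so this cannot be checked.

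**Working it through.** The plan gives no figure on this point, so there is none to reproduce. The check compares the windows and then asks what can be counted.

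**Inputs from the documents**
- Interview window: about 2-6 weeks, so 2 × 7 = day 14 to 6 × 7 = day 42 (Study Endpoints; post-pilot interview procedures).
- Call window: day 0 to about day 15, with no earliest call day (Recruitment Methods).
- Interviews: 200, 100 per arm (post-pilot interview procedures).

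**Inputs the documents do not give (assumptions, shown as ranges)**
- c: the share of calls made before day 14.
- s: the share of interviews begun on the call.

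**Step 1: overlap.** Days 0-15 and days 14-42 share days 14 and 15 only. An interview begun on a call made on days 0 to 13 precedes the window.

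**Step 2: expected early interviews** = 200 × c × s.

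| Calls spread evenly over | c | s = 10% | s = 25% | s = 50% | s = 100% |
|---|---|---|---|---|---|
| days 0-15 | 14/16 = 87.5% | 18 | 44 | 88 | 175 |
| days 7-15 | 7/9 = 77.8% | 16 | 39 | 78 | 156 |
| days 14-15 | 0/2 = 0% | 0 | 0 | 0 | 0 |

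For example, 200 × 0.875 × 0.50 = 87.5, or about 88. The count is also 0 in every row if all interviews are scheduled for day 14 or later. It approaches 200 if nearly all calls come before day 14 and lead straight into the interview. The documents do not narrow this range.

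**Step 3: the late side.** A scheduled interview has no latest day in Recruitment Methods, so one after day 42 is also permitted there. The documents offer nothing from which to count these.

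**Step 4: the arms.** One call rule covers both arms, so early interviews alone need not distort the comparison. The only documented difference is the video requirement for the last 50 intervention participants. Their interview cannot simply continue on the telephone call. Setting them aside leaves 200 − 50 = 150 interviews that could. Time since receipt also matters less for those 50, because they see the materials immediately before answering.

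**The case against.** The strongest reply is that the sections should be read together. The interview procedures and Study Endpoints do set an approximate earliest time; Recruitment Methods merely fails to repeat it. A reader might infer that the plan has no earliest interview day at all, and that would be wrong. The reply does not remove the conflict, because the recruitment text allows the interview to start on the call without reference to that window.

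The timings are also qualified as approximate, and a call at about 15 days is close to two weeks, so staff may intend to call near the opening of the window. That is a fair reading, and it is one of the cases that give 0. It is not the only one, since the text sets 15 days as an upper limit. If the window is loosened to open on day 10, calls spread evenly over days 0-15 still put 10 of 16 (62.5%) before it.

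An interview of about an hour, with consent through an emailed link, makes later scheduling plausible. This stands as a reason not to presume that many interviews would be early. It does not prevent early ones. Finally, this is a small pilot and the analysis text calls the knowledge comparison by arm exploratory, which limits the weight of the point. The same text, however, names knowledge as a primary outcome.

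**Conclusion.** The recruitment text permits interviews outside the window that defines the knowledge outcome, and the passages need to be reconciled. The number affected lies between 0 and nearly all 200 and cannot be narrowed from the documents; each count in the table rests on assumed call timing and an assumed share of on-the-call interviews.

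Two stronger readings are tempting. One is that many interviews would in fact be early; the documents support only that they could be. The other is that the estimated gain in knowledge would be biased by a calculable amount. The documents give no effect size at any time point, and the direction is open: fresh recall would raise the intervention score, while an unopened guide would lower it.

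What stands is a measurement time that may vary and may not match its label, plus less time to open the guide for intervention women not shown the materials at interview. This is a cheap improvement and not a fatal flaw.

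**What to change.** In Recruitment Methods, state that screening and consent may take place on the first call, but that the interview is started or scheduled only within about 2-6 weeks (days 14-42) of receipt of the materials or of randomization to control, with the same rule in both arms. This brings the section into line with Study Endpoints and the interview procedures.

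Record the interview day for every participant and report its distribution by arm. Repeat the knowledge comparison on in-window interviews as a sensitivity analysis, not as a replacement for the main one, since interview day is determined after randomization. If interviews have already been held, the reporting and the sensitivity analysis can still be done wherever interview dates were recorded.

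The cost is a sentence of procedure, one recorded variable and one extra analysis. The downside is that some women will need a second call and a few may not be reached again.
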